Tell participants to allow about 24 hours for payment to be approved. Thank them for coming in and remind them of the following:

1. They should not delete the app off their phone for the full Fall semester. We will be monitoring this remotely and ask them to return to lab if they delete the app.
2. They should cross the intersection of 14th and University at least 4 times a week, and ideally more often.
3. If they have an iPhone and their phone goes dead (e.g. dead battery) or is turned off for some reason, they need to re-start the app. If they don't do this, we will know it remotely and contact them to do it.
4. The app will not do anything for several weeks. At some point later in the semester, they will start getting alerts to remind them not to cross the street while distracted. We cannot tell them when these alerts will start, and it may be different for different people.

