Data Analysis Plan, NCT 03604497

October 9, 2020

Data Analysis. Baseline characteristics were examined descriptively, and then primary analyses were conducted using general estimating equation logistic regressions to account for the dependence of crossing events within participants. The models estimated odds ratios (ORs) and associated 95% confidence intervals (CIs) for the association between the study intervention phase (i.e., pre-intervention, intervention, and post-intervention phases) and distraction (whether visual or aural). Models were adjusted for age, race, distraction prevalence during the pre-intervention phase, and type of phone (i.e., Android or iOS). Given potential for user curiosity at the start of each phase creating changed behavior, a sensitivity analysis was conducted by comparing behavior in the third week of each phase rather than behavior across the full phase.

Next, since anecdotal evidence suggested users were curious about how the alert functioned and therefore used their phone purposely as they approached the intersection, creating artificial datapoints, we conducted analyses stratified by extent of baseline distraction. Finally, we recognized the Android and iOS platforms offered very different alerts to pedestrians, so analyses were conducted to examine whether effect modification by both the prevalence of pre-intervention distraction and phone type was meaningful by including a three-way interaction of intervention phase, distraction category, and phone type in an age- and race-adjusted model examining stratified ORs.

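### If the distraction category comes from the pre-intervention crossings, regression to the mean pushes the low- and high-stratum odds ratios apart even when the alert does nothing

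*SAP*

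**What the plan says.** The first paragraph of the SAP's Data Analysis section models distraction at a crossing by GEE logistic regression. The exposure is study phase, with pre-intervention, intervention and post-intervention levels, and the covariates include each person's distraction prevalence before the intervention. No reference phase is named, but pre-intervention is listed first and is the natural one.

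The second paragraph says that "we conducted analyses stratified by extent of baseline distraction". The reason given is that curious users "used their phone purposely as they approached the intersection, creating artificial datapoints". It then asks whether "effect modification by both the prevalence of pre-intervention distraction and phone type was meaningful", using a "three-way interaction of intervention phase, distraction category, and phone type in an age- and race-adjusted model examining stratified ORs". The SAP does not give the source of the category, the number of categories or the cut-points.

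A sensitivity analysis in the first paragraph is introduced with "Given potential for user curiosity at the start of each phase creating changed behavior" and works by "comparing behavior in the third week of each phase". The Protocol (IV. Payment, reminder 2) tells participants: "They should cross the intersection of 14th and University at least 4 times a week, and ideally more often". The Protocol (II. Questionnaires) also lists a cell phone usage survey at enrolment, but the SAP does not link the category to it.

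**The concern.** The SAP describes the modifier as a prevalence in the pre-intervention phase, which reads as a quantity computed from the app's crossing records. On that reading, the same crossings decide who is a low or a high user and also supply the pre-intervention level of that stratum's odds ratio.

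A person's observed pre-intervention rate is the true rate plus chance. Choosing people because the observed rate was low selects those whose chance error was downward, so their later phases drift up towards the true rate. The reverse holds for people chosen because the rate was high. The stratum odds ratios against the pre-intervention phase then separate around 1 without any effect of the alert.

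The SAP stratifies in order to interpret curiosity and effect modification. An odds ratio above 1 in low users looks like curiosity, and one below 1 in heavy users looks like benefit. The artefact produces both. The SAP describes no separate classification window, shrinkage estimate or untreated comparison group that would remove it.

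**Working it through.** **Inputs.** The plan has no figure to reproduce: the documents give no sample size, distraction rate, crossing count or cut-point. Twelve crossings per phase is 4 a week (the Protocol's instruction) x 3 weeks (inferred from the SAP's third-week analysis) = 12. It is not a guaranteed minimum. All other inputs below are assumptions.

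**Formula.** Let r be a person's observed pre-intervention proportion over m crossings and p the true rate, the same in every phase (no alert effect). In stratum s the later phase has expected rate A = E(p | r in s), and the reference phase has rate B = E(r | r in s). The stratum odds ratio is [A/(1-A)] / [B/(1-B)]. It equals 1 only if A = B.

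**Hand check for single participants.** Take p from a Beta distribution with mean 0.4 and intraclass correlation 0.1, so its two parameters sum to 1/0.1 - 1 = 9. Given y distracted crossings out of m, the expected true rate is (9 x 0.4 + y)/(9 + m) = (3.6 + y)/(9 + m).

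- m = 12, y = 2: expected later odds 5.6/15.4 = 0.364, observed odds 2/10 = 0.2, ratio 1.82.
- m = 12, y = 8: 11.6/9.4 = 1.234, observed odds 8/4 = 2, ratio 0.62.
- m = 60, y = 10: 13.6/55.4 = 0.245, observed odds 10/50 = 0.2, ratio 1.23.
- m = 60, y = 40: 43.6/25.4 = 1.717, observed odds 40/20 = 2, ratio 0.86.

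The direction is fixed, and the size shrinks as crossings accumulate. A stratum averages over many values of y.

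**Simulated strata, no alert effect, equal crossings per phase.** Odds ratios are intervention versus pre.

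| Assumptions | Crossings per phase | Low | High |
|---|---|---|---|
| Logit-normal, SD 1, distraction 20% or 40%, median split | 12 | 1.32-1.62 | 0.75-0.78 |
| Same | 60 | 1.07-1.15 | 0.94-0.95 |
| Beta, mean 0.4, ICC 0.1, median split | 12 | 1.48 | 0.76 |
| Same | 60 | 1.10 | 0.94 |
| Beta, mean 0.4, ICC 0.3, tertiles | 12 | 1.73 | 0.75 |
| Same | 60 | 1.12 | 0.94 |

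Over the whole Beta grid (mean 0.2 or 0.4, ICC 0.1 to 0.5, 12 to 60 crossings), the high-stratum odds ratio was 0.66-0.99. The low-stratum odds ratio was 1.06-3.41 where finite. It was infinite where the low stratum held only people with no observed pre-intervention distraction. The unstratified, unadjusted odds ratio was 1.00 throughout.

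**Three-way model.** An exchangeable GEE with phase x category x phone type plus age and race (300 participants, few runs) gave low 1.26-1.63 and high 0.72-0.78 at 12 crossings, and 1.06-1.18 and 0.92-0.96 at 60. These ranges cover both phone types and include post versus pre.

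**Third-week restriction.** If strata still come from the full pre-intervention phase, comparing only week 3 leaves 1.30-1.66/0.74-0.79 with 4 crossings in that week and 1.07-1.15/0.94-0.95 with 20.

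**Contrast not used to classify.** Post versus intervention within stratum was 0.99-1.01 under the same null.

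**The case against.** **The premise is inferred.** The SAP does not say how the category was formed. If it came from another source, such as the enrolment survey, this problem does not arise. That stands, so the point is conditional. The SAP's own description of the modifier, and its use of pre-intervention prevalence as a covariate, still make the crossing data the more natural source.

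**The size may be modest.** Participants were asked to cross more often than the stated figure if they could. At 60 crossings with a median split, the shift is 7-15% in the low stratum and 5-6% in the high one. This also stands: only the direction is robust.

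**Stronger readings that the documents do not support.**

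- A reader might infer that curiosity or benefit can never be told apart from the artefact. The design has a third phase, and post versus intervention within stratum is free of this mechanism when propensities are stable. An effect that fades once alerts stop would show there. The limit applies to the versus-pre odds ratios taken alone.
- A reader might infer that the SAP's interaction test is invalid. In simulation, a phase x category test at nominal 5% rejected a true null in 20-98% of runs with 100 participants. The SAP does not name that test, and nothing here shows that the three-way term is inflated.
- A reader might infer that the primary result is biased. The unadjusted, unstratified odds ratio is not, and the covariate-adjusted primary model was not examined.

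**Conclusion.** The concern holds in conditional form. If the category is built from the pre-intervention crossings, as the wording suggests, the stratified odds ratios against the pre-intervention phase are biased in opposite directions in the two strata, and so are those read from the three-way model. Those odds ratios alone cannot separate curiosity in low users, or benefit in heavy users, from regression to the mean.

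The null shift is about 1.3-1.6 (low) and 0.75-0.78 (high) at 12 crossings per phase, falling to 1.07-1.15 and 0.94-0.95 at 60. These figures assume 20% or 40% distraction, a between-person SD of 1 logit, a median split and equal crossings. They illustrate the size and do not estimate it for this trial.

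This should be fixed. It affects interpretive analyses that follow the primary ones.

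**What to change.** 1. **Define the category.** State its source, number of levels and cut-points. If the source is not the pre-intervention crossings, say so, and the point falls away.
2. **Separate classification from reference.** If the source is the app data, classify on one part of the pre-intervention phase and use only the held-out part as reference, in both the stratified and three-way models. Split by whole days, for example alternate days, then swap the halves and average, with participant-clustered standard errors. Do not alternate single crossings, because adjacent ones may be alike. With an assumed shared-pair SD of 1 logit and 12 crossings, alternating single crossings left null odds ratios of 1.07-1.09/0.91-0.93, while keeping pairs whole gave 0.99-1.01/1.00-1.01.
3. **Weight if counts differ between phases**, so that each participant counts equally in each phase. With counts independent between phases, a swap by single crossings left 1.04-1.15/0.95-1.01, and weighting brought it to 0.99-1.03/1.00-1.01.
4. **Simple alternative.** Classify on the early weeks and compare week 3 with week 3, without swapping. The null odds ratios stayed at 0.99-1.01, even with early-week distraction 0.3-0.5 logit higher in every phase.
5. **Report post versus intervention by stratum** alongside. It would show an effect that fades after the alerts stop, but not one that fully persists.
6. **State the limits.** The correction assumes that held-out crossings are independent given a stable personal propensity. Person-by-phase drift with SD 0.25 logit left 1.04-1.07/0.96-0.97 after a swap by single crossings, and SD 0.5 left 1.13-1.26/0.85-0.89. Do not read opposite versus-pre stratum odds ratios alone as evidence of benefit or curiosity.

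**Cost.** SAP wording and a re-run on existing data. Simulated standard errors of the stratum log odds ratios, relative to the planned method, were about 0.6-1.2 times for a swap (by single crossings; whole-day splits were not costed), 0.7-1.5 times with weighting, and 1.1-2.0 times for week 3 versus week 3.
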